Informed Consent: The informed consent process will follow the procedures of the WFSM Institutional Review Board. The potential participant is mailed the informed consent form and asked to read it before their initial screening visit. The form is written in simple easy to understand language. At first contact with the prospective participant during the initial screening visit, the study staff member will explain the purpose, methods and extent of the study. We require study staff to review all of the key aspects of the study verbally with the potential participants and to question potential participants to ascertain whether s/he has understood the information. Potential participants are encouraged to ask questions regarding the consent form and the study. Those who are illiterate or have impaired vision must have the consent read to them, followed by opportunity for questions and discussion. A copy of the signed and dated consent form will be given to participants, and the original document will be placed in their individual study file, which will be stored in a secure location. In compliance with the Health Insurance Portability and Accountability Act (HIPAA) and the Standards for Privacy of Individually Identifiable Health Information of the Department of Health and Human Services, we will access personal health information only after obtaining informed consent.

Potential Study Risks: There are inherent potential risks to human subjects who participate in any research study and the potential risks to study participants in this study are listed below.

Any injuries or illnesses (adverse events) during the course of a participant's enrollment in the study are monitored regularly as described in the Data Safety Monitoring Plan.

Assessment risks:

- DXA scans: There are risks with exposure to radiation from the whole body, anterior-posterior spine, and proximal femur DXA scans. The total radiation dose is 45 mRem for baseline and follow-up scans. The potential long-term risk from these radiation doses is uncertain, but these doses have never been associated with any definite adverse effects. Thus, the risk to study participants, if any, is estimated to be slight.
- Physical function tests: There is a small risk of injury during the physical function tests, such as muscle strains or pulls, falls, or joint injury. Risks will be minimized by having experienced/trained staff conducting these assessments. A warm-up and range of motion practice will be conducted before testing. If a participant reports pain, dizziness, or other medical problem, the test will be terminated.
- Blood draw: There is a risk of discomfort, bruising, and/or infection at the sight of puncture for blood drawing. To minimize these risks, blood will be drawn only by trained and experienced phlebotomists who will minimize the discomfort as much as possible and will use good clinical practice procedures to reduce risk of infection.
- Maximal exercise testing is a common procedure with risks, including fainting, dizziness, chest pain, irregular heartbeat, or heart attack, although the latter is extremely rare (<1 death in 10,000 tests) in people with no history of heart disease. The test is monitored by an exercise physiologist and will be stopped if problems occur. Blood pressure, heart rate and rhythm, and breathing will be closely monitored before, throughout, and after the test.

Intervention risks:

1) Risks of weight loss at any age include the concomitant loss of lean (muscle and bone) tissue along with fat mass loss. However, the clinical impact of this muscle and bone loss is not known. Since most adults with obesity have a higher muscle mass and bone density, this risk is mitigated by excluding individuals who are non-obese and less likely to benefit from weight loss and by excluding those with a bone density t-score less than -2.3. In addition, we will assess each participant's 25 hydroxyvitamin D blood level at baseline, 6- and 18-months; if found to be deficient (< 20 ng/mL) a participant will be referred to his/her primary care physician for follow-up assessment and supplementation before beginning the study intervention. During the behavioral weight loss classes, we will also provide nutrition education regarding adequate intake of calcium and Vitamin D, including encouraging use of dietary supplements. Participants will be counseled to consume, either using food or dietary supplements, at least 1300 mg of calcium and 1000 IU of Vitamin D daily.

Finally, if any participant experiences a bone density decline (either at hip or spine) of $\geq 10\%$, or has a t-score of < -2.5 , at the 6-month DXA assessment, she/he will be counseled to stop their caloric restriction and will be referred to his/her primary care physician.

2) The risks of the structured exercise intervention may include: 1) musculoskeletal complications and muscle soreness in the early phases of the intervention, 2) an increased fall risk, and 3) increased risk of hypoglycemia or hyperglycemia, especially in participants with type II diabetes on insulin or short-acting insulin secretagogues.

Musculoskeletal and fall risks are minimized since all center-based exercise sessions will be supervised by trained exercise staff who will instruct participants in proper treadmill walking and balance safety, proper footwear, and in selection of safe walking areas outside of the center.

Hypoglycemia/hyperglycemia risks will be mitigated by following the recommendations of the American College of Sports Medicine and American Diabetes Association for safety precautions of exercise in patients with diabetes.⁹⁹ Specifically, risks will be reduced by educating participants of this risk, by discussing signs and symptoms for them to be aware of prior to, during, and after an exercise bout, and by encouraging proper nutrition and hydration prior to exercise. For center-based sessions, we will have easily digestible snacks, glucose tablets, and juice in the exercise center and we will encourage them to have one of these carbohydrate sources accessible during their home-based sessions. Participants who use insulin or short-acting insulin secretagogues for blood glucose control will have their blood glucose checked via glucometer before and after exercise at the supervised sessions and will be encouraged to do this for their home-based exercise. If a participant's glucose is <100 mg/dl we will require them to consume a snack containing about 15 grams of carbohydrate prior to exercise; if it is >300 mg/dL they will be encouraged to hydrate and postpone exercise until their blood glucose level is below 300 mg/dL. We will also encourage participants to monitor their glucose after exercise to determine if food consumption or medication changes should be made. In some cases, we may ask a participant to consult with their physician about reducing medication dosage prior to an exercise session.

3) Risks of the SitLess intervention are minimal, but also may include an enhanced fall risk. This will be minimized by reviewing environmental factors that are known to increase fall risk.

Confidentiality and Privacy

Confidentiality will be protected by collecting only information needed to assess study outcomes, minimizing to the fullest extent possible the collection of any information that could directly identify study participants, and maintaining all study information in a secure manner. To help ensure subject privacy and confidentiality, only a unique study identifier will appear on the data collection form. Any collected patient identifying information corresponding to the unique study identifier will be maintained on a separate master log. The master log will be kept secure, with access limited to designated study personnel. Following data collection subject identifying information will be destroyed at the earliest opportunity, consistent with data validation and study design, producing an anonymous analytical data set. Data access will be limited to study staff. Data and records will be kept locked and secured, with any computer data password protected. No reference to any individual participant will appear in reports, presentations, or publications that may arise from the study.

Data and Safety Monitoring

The co-PIs, along with the study physician, will be responsible for the overall monitoring of the data and safety of study participants. In addition, all clinical intervention studies conducted by Aging Center investigators are monitored by the WFU Claude Pepper Older Americans Independence Center's NIH-approved Data Safety Monitoring Board (DSMB). Finally, the external NIA-appointed Data and Safety Monitoring Board (DSMB) will have overall responsibility of independently monitoring all aspects of the study, including those that require access to any un-blinded data. This committee acts in an advisory capacity to the NIA to monitor participant safety, evaluate the progress of the study, review procedures for maintaining the confidentiality of data, and the quality of data collection, management, and analyses. The

DSMB will have access to all study data, documents and progress information, and will be notified of all changes that are made to the protocol.

Reporting of Unanticipated Problems, Adverse Events or Deviations

Any major AE, i.e., any serious injury, including all SAEs, will be recorded and reported to the co-PIs immediately after completing any and all actions that are necessary to protect the subject's health and safety. Minor AEs will be recorded and reported within seven days. A description of the event, and the date and location of the event will be recorded on the AE Reporting Form. The PIs and the Medical Director will meet quarterly, or as needed, to review all reported events and these will be compiled and reported in aggregate to the DSMB at each biannual meeting of the DSMB.

Within 24 hours of notification of any SAE, the PIs will report the event to the WFSM Institutional Review Board (IRB). If the event occurred as a direct result of participation in this study, an amendment will be made to the consent form and the co-PIs will request new IRB approval. The SAE will also be reported within 24 hours to the NIA and Chair of the DSMB via a verbal phone call, or by a report submitted by fax or email.

Use of biological samples by other investigators

Biological samples may be used by investigators other than the investigators of the current study. The use will be limited to non-commercial purposes. The names and other personal identifiers of the study participants will not be sent to any recipients of the blood samples.

Storage and disposal of biological material

Blood samples will be stored at Wake Forest University Medical Center for up to twenty years after the end of the trial at which time the samples will be destroyed. Biological specimens will be stored in locked -70°C alarmed freezers located in a locked room. The lab coordinator and the PIs have access to the keys of the freezers. All the specimens will have numerical study IDs with no personal identifiers of the participants. These are stored under the Pepper Center Tissue Repository (IRB#1219).

References

1. Executive summary: Guidelines (2013) for the management of overweight and obesity in adults: a report of the American College of Cardiology/American Heart Association Task Force on Practice Guidelines and the Obesity Society published by the Obesity Society and American College of Cardiology/American Heart Association Task Force on Practice Guidelines. Based on a systematic review from the The Obesity Expert Panel, 2013. *Obesity (Silver Spring)* 2014;22 Suppl 2:S5-39.

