refraining from food, beverages (with the exception of water), alcohol and caffeine. Before any data collection, participants provide written informed consent and complete a HIPAA authorization form in accordance with our IRB policy. At this visit, weight and height will be measured to calculate BMI. Individuals who meet the BMI criteria will undergo a medical history and a cognitive test (MoCA). The medical history (including blood pressure, review of medications, and a fasting blood draw for metabolic panel, vitamin D level, and blood cell count) will exclude those with recent history of coronary heart disease, cancer, liver or renal disease, severe pulmonary disease, gross physical impairment, uncontrolled hypertension, or any contraindications to exercise. The fasting blood profile will exclude those with uncontrolled diabetes,⁶⁹ anemia, or liver, renal, or hematological dysfunction. Individuals with abnormal results at screening will be referred to their physicians. Prior to randomization, eligible participants will be asked if they would like to participate in an MRI ancillary study. This is visit 2.1 listed in the table on page 7. Refusal to participate in the ancillary study will not exclude them from the main (parent) study. See Appendix A for details of the MRI ancillary study. Eligible participants will be randomized to treatment using a web-based randomization scheme developed by the biostatistician, stratified by sex with random block sizes.

Study Interventions

Weight Loss intervention: 9-mo WL phase—All participants will undergo a dietary WL intervention designed to elicit behavioral changes leading to decreased caloric intake sufficient to yield a ~10% loss of initial body mass. The WL intervention includes nutrition education, state-of-the-art behavioral methods for promoting WL, and strategies that optimize self-regulation.^{8, 70, 71} During the intensive phase of WL (months 1-6), participants will meet in weekly group sessions delivered by either the RD or staff trained on specific elements of the intervention with individual sessions possible on an as needed basis. These group meetings will transition to bimonthly group meetings during months 7-9 and to monthly follow-up phone/email contact during the follow-up phase (months 10-18).

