The Fitbit and website are used to induce behavior change over the course of the intervention; participants begin wearing the Fitbit daily for the first 9 months and then wear time is tailored to each individual for the remainder of the study, however, we ask that all participants use the devices at least 2 days each week as described above.

The SitLess intervention counseling sessions occur in conjunction with the WL sessions and follow the same contact schedule to achieve treatment goals. Participants meet weekly during the first 6 months and bimonthly during months 7-9. These sessions will focus on: (1) reviewing data from the activity monitors, (2) reinforcement for observed changes in behavior, and (3) motivational interviewing and problem solving to increase commitment to change and assist with overcoming barriers.⁷³ The goal is to build commitment to the use of the devices and to link the feedback to improvements in personally-valued outcomes in their daily lives.

9-mo Follow-up phase—During this phase, participants will receive a monthly phone call or email contact for the purpose of emphasizing adherence to the SitLess goals and the Fitbit activity tracking and associated website.

Aerobic exercise intervention: 9-mo WL phase—Participants in the WL+EX and WL+EX+SitLess treatment arms will be asked to perform structured aerobic exercise (mostly treadmill walking) of moderate-intensity for 4-5 days/week, progressing to a duration of 200

min/week. Participants will attend center-based sessions for at least 3 days/week during the first intensive 6-month phase and at least one day/week during the second 3-month transition phase (months 7-9), with recording of home-based exercise for the other 2-4 days/week. The rationale for, background education on exercise training, and monitoring of study progress occurs in conjunction with the WL sessions in a manner consistent with the SitLess intervention. The level of exercise is based on current public health recommendations from the American Heart Association and American College of Sports Medicine (ACSM) for optimizing cardiovascular fitness in older adults,⁷⁴ and the ACSM recommendation for appropriate physical activity strategies for WL.⁷⁵

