Participants in all three groups will receive a Fitbit activity monitor, prior to the start of intervention, to assist with self-monitoring of their prescribed activity (e.g., aerobic exercise and/or decreased daily SB). As stated above, they will be encouraged to wear the Fitbit daily during the 9-month WL phase, and to wear it at least twice/week during the 9-month follow-up phase. If the monitor is lost, stolen or damaged they will be provided with a replacement. If a participant withdraws from the study, they will be asked to return the Fitbit. After completion of the last study visit, participants will be allowed to keep the Fitbit.

In addition, the study interventions require the use of a smartphone to upload data from the Fitbit and to access the study website to receive encouragement and motivation. If a participant does not own a smartphone or their smartphone is not compatible with our applications, the study will provide them with a smartphone and a phone/data plan for the length of their participation in the

study. Participants will be expected to keep the phone with them daily and to take care not to lose or damage it. Participants will be instructed that the phone is for study use only. If the phone is lost, stolen or damaged they will be provided with a replacement. If a participant withdraws from the study, they will be asked to return the smartphone and it will be deactivated immediately. After completion of the last study visit (V8), participants will return the smartphones and they will be deactivated.

Schedule of assessment visits

Assessments at baseline, after the intensive WL phase (6-months), after the entire 9-month WL intervention (9-months) and at study end (18-months) include: the primary outcome of body weight, as well as physical activity energy expenditure, light, moderate and vigorous activity minutes, and sedentary behavior minutes and breaks. The other secondary outcome assessments (RMR, physical function and measures of cardiometabolic risk) will be performed at baseline, after the intensive WL phase (6-months), and at study end (18-months) (See Table). At follow up, Visit 7 and 8 may be combined to help with participant burden and some questionnaires will be administered over the phone to limit the time in the clinic.

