The nature, purpose, and risks of all tests will be explained to participants prior to obtaining their written consent and prior to each test. All examiners will be blinded to participant treatment assignment and are trained in the standardized conduct of all tests. Standardized written instructions will be provided.

Study Measure(s)

1. Baseline demographic data will be recorded based on participant self-report. Medical information on prior and existing co-morbidities and hospitalizations will be ascertained by self-report and confirmed by direct query of the participant at the screening visit. We will also record medication use by asking participants to bring in all medications (including nutritional supplements).
2. Adverse events will be assessed by asking participants at each assessment visit, and during monthly phone or email contact with participants during the 9-month follow-up phase, to report any health changes, injuries, etc. and these will be recorded using the Adverse Event Form.
3. Body weight and composition: Body weight (the study's Primary Outcome) will be measured in our clinic on the same scale. Body composition, bone density, visceral fat will be measured by dual-energy X-ray absorptiometry (DXA; Hologic Discovery W, Bedford, MA). All scans will be performed and analyzed by our trained DXA technician who is certified by the International Society for Clinical Densitometry. Bone mineral density (BMD) will be measured using specific scans of the anterior-posterior spine (L1-L4) and proximal femur. Visceral fat area will be measured from the whole-body scan in a 5-cm wide region across the entire abdomen just above the iliac crest at a level approximate with the 4th lumbar vertebrae.⁷⁷
4. Resting metabolic rate will be assessed to determine participant's weight-maintaining energy needs for prescribing the 400 kcal/d energy deficit for WL and will be measured again at 6- and 18-months to determine its response to the interventions. RMR will be measured in the morning after an overnight fast (8 hour minimum of no food, beverage, alcohol, caffeine or strenuous exercise) by indirect calorimetry.⁴¹ Upon arrival, subjects are asked to lie quietly for 20-30 min before testing. Measurement of oxygen consumption and carbon dioxide production are collected continuously for at least 30 min and RMR is calculated using the Weir equation.⁷⁸

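### After baseline, adverse events in the 9-month weight-loss phase are asked about only at months 6 and 9; capture between visits is unprompted and may be less complete in WL+SitLess

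*Combined protocol and SAP*

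**What the plan says.** Study Measure(s), item 2, names two occasions for asking about adverse events: "Adverse events will be assessed by asking participants at each assessment visit, and during monthly phone or email contact with participants", the contacts being those of the 9-month follow-up phase. The Schedule of assessment visits fixes the first of these: "Assessments at baseline, after the intensive WL phase (6-months), after the entire 9-month WL intervention (9-months) and at study end (18-months". The Weight Loss intervention section fixes the second, placing "monthly follow-up phone/email contact during the follow-up phase (months 10-18" after the group meetings have ended.

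Staff contact in the weight-loss phase is described separately. In months 1-6, in every arm, "participants will meet in weekly group sessions delivered by either the RD or staff", and body weight is recorded at each session. SitLess counselling is delivered with those sessions: "Participants meet weekly during the first 6 months and bimonthly during months 7-9". For the two exercise arms there is more: "Participants will attend center-based sessions for at least 3 days/week during the first intensive 6-month phase", then at least one such day a week in months 7-9. Under Intervention risks, users of insulin or short-acting secretagogues also have glucose checked before and after supervised exercise. No section says that adverse events are asked about at group or exercise sessions.

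On oversight, the Reporting section says: "Minor AEs will be recorded and reported within seven days". It adds quarterly review by the principal investigators and Medical Director, and aggregate reports to biannual DSMB meetings. Potential Study Risks says that events are monitored regularly, without giving an interval.

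**The concern.** Questioning is sparsest when the interventions are most demanding. Caloric restriction starts in months 1-6, and supervised exercise reaches its full prescription by the end of week 6. The protocol itself places musculoskeletal complications and soreness early in the intervention. Participants are 65-85 years old. An event in this period that nobody prompts for may be reported months late, or not at all.

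The gap may also differ by arm. Where capture depends on a participant mentioning something to staff, more staff contact gives more chances to mention it. Falls are listed as a risk of both exercise and SitLess, so a fair comparison needs equal ascertainment. The rationale section argues that older obese adults tolerate and sustain exercise less well. Under-detection in WL+SitLess would shift any tolerability comparison toward that expectation.

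**Working it through.** The plan gives no figure to reproduce here. The check counts scheduled queries and minimum scheduled contacts, taking 6 months as 26 weeks and 3 months as 13 weeks.

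**1. Scheduled adverse-event queries per participant after baseline (same in every arm)**
- After baseline and before the 6-month visit: 0
- 6-month visit: 1
- Between the 6- and 9-month visits: 0
- 9-month visit: 1
- Months 10-18: 9 monthly contacts + the 18-month visit = 10

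The weight-loss phase has 2 queries and the follow-up phase has 10. The longest unqueried intervals are 6 months, 3 months and about 1 month in turn.

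**2. Against the oversight timetable**
- Quarterly review: 6 ÷ 3 = 2 review cycles fit into the first unqueried interval. A participant can pass through at least one review with no solicited data after baseline. With biannual read as twice a year, the same can happen at a DSMB meeting.
- The seven-day rule is a recording deadline, not a query schedule. An event early in month 1 may not be asked about for up to 26 × 7 = 182 days.

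**3. Minimum staff contacts, months 1-6**
- WL+SitLess: 26 × 1 = 26 group sessions
- Exercise sessions in WL+EX and WL+EX+SitLess: 26 × 3 = 78
- If one exercise day each week coincides with the group session, the exercise arms have 78 contact days: 78 ÷ 26 = 3
- If all are on separate days: 78 + 26 = 104; 104 ÷ 26 = 4

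The exercise arms therefore have 3 to 4 times the contacts. In months 7-9 they have at least 13 × 1 = 13 center days, on top of group meetings held in all arms. These are scheduled contacts, not attended ones.

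**4. What unequal capture could do (every rate here is assumed)**

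Let *c* be the share of events captured between visits and *r* the share of the remainder recovered at the 6-month visit. Detected share = *c* + (1 − *c*)*r*. Assume equal true rates, *c* = 0.8 in the exercise arms, and *c* = 0.5 or 0.2 in WL+SitLess.

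| *r* | Exercise arms | WL+SitLess, *c* = 0.5 | Ratio | WL+SitLess, *c* = 0.2 | Ratio |
|---|---|---|---|---|---|
| 0 | 0.80 | 0.50 | 1.60 | 0.20 | 4.00 |
| 0.5 | 0.90 | 0.75 | 1.20 | 0.60 | 1.50 |
| 0.8 | 0.96 | 0.90 | 1.07 | 0.84 | 1.14 |
| 1.0 | 1.00 | 1.00 | 1.00 | 1.00 | 1.00 |

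The distortion runs from none to large, depending on capture and recall rates that the documents do not give.

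**The case against.** The strongest reply is that the plan does expect capture between visits and gives every arm a channel for it. Group sessions are weekly, and the dietitian reviews diaries weekly. SitLess staff can phone or email participants, and the website is a further route. The seven-day rule is not limited to events found at visits. The 6- and 9-month visits then put the same question to all arms. Adverse events appear in no aim and no planned analysis, and DSMB reports are described as aggregate. The visit table and any separate Data Safety Monitoring Plan are not in the text available, so a further query may be listed there.

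Much of this stands. A reader might infer that safety review rests on spontaneous reports alone. It does not, because the equal 6- and 9-month queries cover the whole weight-loss phase by recall. A reader might also take 4:1 as the imbalance in detection. It is the upper end of a range of contacts, and WL+SitLess participants, seen weekly, may report most of what happens. Nor is this exercise against SitLess in general: WL+EX+SitLess has the same supervised sessions as WL+EX, so contact is unequal only in comparisons with WL+SitLess.

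The reply does not supply a prompt. A channel through which events can be mentioned is not a question that is asked, and item 2 lists specifically when the question is asked. Recall at 6 months may recover an event, but it cannot make the report timely. If another document adds a query, item 2 needs reconciling with it.

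**Conclusion.** The point holds as a weakness in the stated schedule. In the text available, the weight-loss phase has 2 solicited queries after baseline against 10 in follow-up, with unprompted intervals of 6 and 3 months. That does not serve seven-day recording or quarterly review well. The exercise arms have about 3-4 times the staff contacts of WL+SitLess in months 1-6 and an arm-specific route for detecting glucose problems. Under-detection in WL+SitLess relative to WL+EX and WL+EX+SitLess is therefore possible.

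Its size is unknown. The contact counts assume 26 weeks, the stated minimum of exercise sessions and full attendance; the detection ratios rest on assumed rates. A reader might go further and infer that the DSMB will see a table in which exercise looks worse through detection alone. The documents do not support that as a finding. The DSMB may have access to unblinded data, so a comparison by arm could be made, but no by-arm safety table is described and nothing quantifies a bias.

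**What to change.** Amend Study Measure(s), item 2, so that the same scripted adverse-event question is asked at the group sessions that all arms attend in months 1-9, and record the answers on the existing Adverse Event Form.

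- Ask it individually, for example at the weigh-in, and word it to cover the time since the participant was last asked, so that a missed session leaves no gap.
- Keep to the script. Staff running the sessions will know the treatment arm.
- State whether bimonthly in months 7-9 means twice a month (about 6 sessions) or every two months (1 or 2), because this sets how often the question is asked.
- Base any between-arm tabulation on events from the common queries: group sessions, assessment visits and monthly contacts. List events noted only at exercise sessions separately; keep them for safety review.

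The cost is a protocol amendment, a few minutes per session and more minor events to log. The interventions do not change.
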